Retention: With n=35 per treatment condition, the 95% confidence interval (CI) for the estimated retention rate in each condition will be within $\pm 11.8\%$ if the observed retention is 85%. Thus, given n=35 per condition, the lower limit of the 95% CI for the observed retention rate in either treatment condition should not be lower than 73.2%. App use: With n=35 per treatment condition, the lower limit of the 95% CI for observed proportion of 80% of participants meeting targets for app use in either treatment condition should not be lower than 66.7%. Acceptability: Assuming 85% retention, with n=30 available per treatment condition, the lower limit of the 95% CI for observed proportion of 80% of participants providing high acceptability ratings in either treatment condition should not be lower than 65.7%. Exploratory outcomes: We propose 6-month change in weight, 6-month change in weight loss problem solving, counselor time, and group cohesion at 6 months as exploratory because a true test of efficacy will require a fully powered trial informed by the refined procedures that will result from this feasibility study. Since the primary focus of this pilot trial is to assess feasibility to inform the design of the subsequent efficacy trial and the trial was powered to assess feasibility, not demonstrate efficacy, we only have 80% power to detect differences far larger than we expect to find in the subsequent efficacy trial. For example, taking an intent-to-treat approach, we have 80% power to detect differences of ≥ 0.68 SDs in weight change and the other exploratory outcomes. For example, if the SD=6.0%^{10,11} weight loss, we only have 80% power to detect differences in percent weight loss $\geq 4.1\%$, a difference 1.5-4 times larger than observed in previous research.

How are participants recruited?

Participants will be notified or approached about this research study through digital ads on various platforms (e.g., search engines, health websites, and social media platforms). One method we may use will be in collaboration with a company called Build Clinical. Build Clinical is a technology company that enables academic researchers to engage the exact populations needed for a given study.³⁸ Build Clinical will create the advertisements and landing page as well place the digital ads on the various platforms across the Internet. Participants will learn about the research study through these digital ads that will appear

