During the 6-months of the intervention, the program will have monthly breakout sessions for participants to join via WebEx or within Facebook “rooms.” Each month, the counselor and/or study staff will schedule a 45-minute event within the Facebook group that will allow participants to RSVP to, if they so wish. When they click on the event on the day/time it was scheduled for, they will be brought to the events tab in the Facebook group where they can click on the WebEx link and/or internal Facebook link to bring them to the breakout session. The counselor and/or staff member will be leading the sessions. Each month will be based on a topic around achieving a healthy lifestyle (or barriers to achieving a healthy lifestyle). The participants will have the option pick the topic for each week if they’d like. If not, the study team will pick a topic. The counselor will talk about the topic of the month and will promote discussion between participants. As needed, the counselor will pose discussion questions related to the topic of the week to help facilitate the discussion. The meetings will be recorded and posted in the Facebook group for those who missed. If they do not wish to be recorded, they will be able to leave the meeting and watch the video after it is posted in the group or turn their video off. The point of these breakout sessions is for group members to connect on a topic, do some brainstorming, and get to know each other better.

2. Facebook Group

Participants will be asked to join a private Facebook group where they will receive weight loss counseling based on the Diabetes Prevention Lifestyle Intervention (DPP). The Habit and calorie tracking app conditions will each have their own Facebook group. The group leader will counsel participants toward achieving and maintaining the exercise and diet goals to lose weight. The participants will also be asked to participate in the Facebook group by reading and engaging with the posts from the counselors. Additionally, they will be asked to engage with their fellow participants through comments, reactions, and posts. The participants will be able to privately message their counselor if they do not want to share something with the group. A detailed description of the how the Facebook group will operate is below.

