Follow-ups. Follow-ups are completed after the intervention ends. Participants will receive a link to an online REDCap follow-up survey in the beginning of the week following the end of the intervention. This survey will be a repeat of some of the measures assessed at baseline (indicated in the measures table below) and questions to solicit participants' feedback on the program and app. The participants will also weigh-in one final time after the intervention ends. Finally, the participants will schedule and attend a focus group call lead by study staff to get their feedback on their experience in the intervention.

Focus groups. A focus group will occur in a WebEx setting starting the week after the end of the intervention. The focus group will last for approximately 30-60 minutes (depending on how many participants are in attendance) and will include a discussion about likes and dislikes of the intervention as well as their opinion on various features of the app and intervention. All focus groups will be conducted via WebEx including 1-4 participants on each call. Any participants who are unable to attend the focus group will receive the focus group questions through an e-mailed survey. We will e-mail the survey twice. At the time of the 2nd e-mail, we will also text them to let them know to check their e-mails. If there is no response from the participant after the 2nd e-mail, we will make no further attempts to contact them. The focus groups will be recorded on WebEx and then will be transcribed using Otter.ai, a web-based transcription software.

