Patient Health Questionnaire (PHQ)-8: The PHQ-8 is an 8-question measure like PHQ-9 (with the omission of one question). The Cronbach's α for the PHQ-8 was 0.88 which demonstrates good reliability and a Spearman coefficient of 0.616 which demonstrates good convergent validity when compared to the PHQ-9.⁴⁸ Together, this data shows the PHQ-8 is as valuable as the PHQ-9.

Social Problem-Solving Inventory-Revised: The internal consistency reliability (Cronbach's α 0.95) was high. The SPSI-R score was significantly associated ($p < .05$) with various subscales from calories, exercise, distress, and quality of life suggesting concurrent validity.⁴⁹

The User Engagement Scale Short Form (UES-SF): The UES-SF has shown to be statistically reliable ($\omega = 0.88$).⁵⁰ Furthermore, each subscale highly correlates with the remaining items in the scale. This suggested that each subscale can accurately represent the value of the

components from which the subscales were derived. Accordingly, these items were defined to be the UES-SF and were taken forward for evaluation.⁵⁰

Group Climate Questionnaire Short: The GCQ-S is a 12-item questionnaire with 3 subscales: engagement, avoidance, and conflict.⁵¹ Construct validity of the GCQ has been comprehensively examined and has been shown to be strong.⁵²⁻⁵⁵ Cronbach alpha levels for the subscales of the GCQ were high at .94 for engagement, .92 for avoidance, and .88 for conflict.⁵⁶

Analytic Plan

Data will be analyzed using an intent to treat approach. For missing data, we will perform a series of sensitivity analyses to understand the extent of potential bias by assuming the subjects who dropped out are (i) missing completely at random (i.e., independent of the outcome), (ii) are responders to the intervention, or (iii) are non-responders to the intervention. If more than 5% data missing, we will use multiple imputation.⁵⁷ We will use IBM SPSS Statistics for Windows, Version 27.0. (Armonk, NY: IBM Corp.) and STATA 17 (College Station, TX: StataCorp LLC.).

Recruitment. We will report numbers and reasons for exclusion using a CONSORT diagram,^{60, 61} and we will compare recruitment sources by gender and race/ethnicity yields.

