App use. In the Habit app condition, descriptive statistics will be performed to summarize the number of days participants used each feature. These numbers will be inspected relative to the use targets defined for each feature. In the MyFitnessPal condition, descriptive statistics will be performed to summarize the mean number of days participants used MyFitnessPal over the 6-month intervention. A total “app compliance” score will be developed for each participant based on the percent of days they completed of their assigned use. Exploratory analyses using ANOVAs will compare conditions on app compliance scores at 6 months.

Retention. We will calculate retention as the proportion of participants who complete the 6-month follow-up assessment in each condition and report this information using a CONSORT diagram.

Engagement. Number of Facebook reactions (e.g., like, care, wow, etc.), replies, posts, and polls per participant during the 6-month program.

Acceptability. We will report participant satisfaction.

Burden. Using descriptive statistics, we will summarize burden scores in both treatment conditions. ANOVAs will be used to compare conditions on burden.

Group Cohesion. Using ANOVAs, we will compare conditions on group cohesion and climate total and subscale scores at 6 months.

Contamination. We will report the percent of participants that used any outside programs that provided weight loss coaching/problem solving.

Weight Change (exploratory). We will calculate weight changes from baseline to 6 months in each treatment condition. We will compare percent weight change from baseline to 6 months across the two treatment conditions using a mixed effects model approach with weight as the continuous outcome variable, and time as a covariate using percent weight change calculated from all available objectively measured weekly weights. To adjust for within-subject correlation in the mixed model, first we will estimate an unstructured within-subject covariance matrix; estimates may suggest that a simpler structure, e.g., compound symmetry (random intercept) is satisfactory.

Changes in weight loss problem solving. Using a mixed effects model with weight loss problem solving as the continuous outcome variable, we will compare conditions in change in weight loss problem solving from baseline to 6 months.

Group cohesion. Using ANOVA, we will compare conditions on group cohesion measures at 6 months.

Study Removal

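### The stated 80% power at 0.68 SD does not hold for group cohesion at 30 per arm, the follow-up number the same paragraph assumes: about 74% power, or 0.74 SD at 80% power

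*Combined protocol and SAP*

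**What the plan says.** All the planning figures stand in one paragraph of the combined protocol and SAP, under *How was sample size determined?*

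- **Power.** The plan states that "taking an intent-to-treat approach, we have 80% power to detect differences of ≥ 0.68 SDs in weight change and the other exploratory outcomes". The exploratory outcomes listed just before are 6-month change in weight, 6-month change in weight loss problem solving, counselor time, and group cohesion at 6 months. The example that follows turns 0.68 SD into a 4.1% difference in weight loss at an SD of 6.0%. Neither the significance level nor the test is given.
- **Number available.** For acceptability the paragraph uses a smaller number: "Assuming 85% retention, with n=30 available per treatment condition". Retention and app use are planned on 35 per condition.
- **Meaning of retention.** In the Analytic Plan, under Retention: "We will calculate retention as the proportion of participants who complete the 6-month follow-up assessment in each condition".
- **Group cohesion.** The Measures table schedules the group climate questionnaire at follow-up only, with no baseline or interim administration. The Analytic Plan compares conditions on it at 6 months by ANOVA.
- **Missing data.** The Analytic Plan adopts an intent-to-treat approach with sensitivity analyses, and adds: "If more than 5% data missing, we will use multiple imputation".
- **Grouping.** Under Intervention, Facebook Group: "The Habit and calorie tracking app conditions will each have their own Facebook group".

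**The concern.** Two measures collected after the intervention ends are planned on different numbers in the same paragraph. Acceptability is given 30 per arm because some participants are expected to miss follow-up. Group cohesion comes from the same follow-up survey, but is covered by a power figure that needs 35 per arm. A participant who does not return the survey has no cohesion score.

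At stake is how far the power sentence can be relied on for a named outcome. Someone using the pilot to plan the efficacy trial would read 80% power at 0.68 SD for group cohesion, which the plan's own retention assumption does not support.

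**Working it through.** **Inputs**

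| Input | Value | Source |
|---|---|---|
| Randomised per arm | 35 | Sample size section |
| Assumed retention | 85%; 0.85 × 35 = 29.75, taken as 30 | Sample size section, acceptability |
| Power and detectable difference | 80%, 0.68 SD | Sample size section, exploratory outcomes |
| Analysis of group cohesion | ANOVA on two conditions (same as a t-test) | Analytic Plan, Group Cohesion |
| Alpha | 5%, two-sided | Assumed; not stated in the plan |
| Participants independent | Yes | Assumed; not stated in the plan |

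**Formula.** With n measured per arm and a standardised difference d, the t statistic has 2n − 2 degrees of freedom and noncentrality d × √(n/2). Power is the probability that it exceeds the two-sided 5% critical value in absolute size. The detectable difference is the d at which that probability is 80%.

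**Step 1: reproduce the plan's figure (n = 35).**
- Degrees of freedom 68, critical value 1.995.
- Noncentrality at 0.68 SD: 0.68 × √17.5 = 2.845.
- Power at 0.68 SD: 80.1%. Detectable difference at 80% power: 0.679 SD.
- 0.68 × 6.0% = 4.08%, which is the plan's 4.1%.
- With 34 per arm the exact power is 78.9%, so 0.68 SD needs all 35. A one-sided 5% test at 35 per arm would give 0.60 SD and does not explain the stated figure.

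**Step 2: confirm that the plan itself uses 30 for a follow-up measure.** The acceptability limit is 0.80 − 1.96 × √(0.80 × 0.20 / 30) = 0.657, the stated 65.7%. The app-use limit uses 35: 0.80 − 1.96 × √(0.80 × 0.20 / 35) = 0.667, the stated 66.7%. So the paragraph already separates what is known for everyone from what depends on follow-up.

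**Step 3: apply 30 per arm to group cohesion.**
- Degrees of freedom 58, critical value 2.002.
- Noncentrality at 0.68 SD: 0.68 × √15 = 2.634.
- Power at 0.68 SD: 73.6%. Detectable difference at 80% power: 0.736 SD.

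**Step 4: check by the normal approximation.** The detectable difference is (1.960 + 0.842) × √(2/n), which is 0.670 SD at 35 and 0.723 SD at 30. Power at 0.68 SD is 81.2% and 75.0%. The drop is about the same size.

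| Measured per arm | Detectable at 80% power | Power at 0.68 SD |
|---|---|---|
| 35 | 0.68 SD | 80% |
| 33 | 0.70 SD | 78% |
| 32 | 0.71 SD | 76% |
| 30 | 0.74 SD | 74% |

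The rows for 32 and 33 show the result if survey return is better than 30 per arm. They are not figures from the plan.

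**The case against.** **The basis is declared.** The sentence invokes intent-to-treat, which points to all 35 randomised, so it can be read as a correct calculation on a stated basis. The arithmetic is indeed right at 35. But intent-to-treat settles who is analysed, not whether a score exists. Group cohesion has no baseline or interim value from which to impute, and the plan names no strong auxiliary predictor, so multiple imputation would restore little.

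**Thirty is an assumption.** The 85% is conditional, and the paragraph applies it only to acceptability. The follow-up assessment consists of a survey, a weigh-in and a focus group. If retention means completing all three, more than 30 per arm could return the survey. On the other hand, participants may skip questions. This stands: 30 is the plan's working figure for a comparable measure, not a fixed number for cohesion. At 32 or 33 per arm, power at 0.68 SD would be 76% to 78%, still short of 80%.

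**The consequence is slight.** The paragraph is itself arguing that power for these outcomes is inadequate, and a larger detectable difference strengthens that argument. This also stands.

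**Stronger readings the documents do not support.** A reader might infer that the whole 0.68 SD statement fails.
- *Weight change.* The planned analysis is a mixed model "using percent weight change calculated from all available objectively measured weekly weights", so participants lost before 6 months still contribute. A comparison of 6-month completers only is not what the plan proposes, and the 4.1% example is not shown to be wrong.
- *Counselor time.* It need not depend on participants returning the follow-up survey.
- *Change in problem solving.* This has a baseline value, and the Analytic Plan does not say how its mixed model treats it. Take 30 follow-ups per arm and assumed baseline to 6-month correlations of 0.3 to 0.9. Power at 0.68 SD of change is then about 76% down to 74% with separate baseline means, and about 89% down to 76% with baseline adjustment. Neither a shortfall nor adequate power can be asserted.

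**Conclusion.** The point holds for group cohesion and is minor. The plan states 80% power at 0.68 SD for an outcome collected only at follow-up. With the 30 per arm that the same paragraph assumes for acceptability, power is about 74% and the detectable difference about 0.74 SD.

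This rests on three assumptions: a two-sided 5% t-test, chosen because it reproduces the plan's figure; about 30 cohesion scores per arm; and independent participants. The third applies equally to the figure at 35 per arm. Each condition is one Facebook group whose members interact, and the plan does not say that its power figure ignores this.

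Nothing in the trial's conduct or main conclusions turns on it. The outcomes concerned are labelled exploratory, the plan says it is not powered for efficacy, and 70 was chosen to form two online groups of 35.

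**What to change.** Replace the 0.68 SD sentence in the sample size section with wording such as:

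*With a two-sided 5% t-test treating participants as independent, 80% power corresponds to 0.68 SD with all 35 per arm measured; for group cohesion, collected only at follow-up, it corresponds to about 0.74 SD if 30 per arm are available at 85% retention.*

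This states the test, the alpha, the number behind each figure and the independence assumption, and brings group cohesion into line with acceptability. The cost is a text edit, with no change to enrolment, procedures or analysis. The one downside is that a stated figure becomes slightly less favourable.

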Study Protocol and Analytic Plan
for Building Habits Together Online Weight Loss Program
NCT06154213
October 1, 2021

Study Protocol

Background

Technology-delivered weight loss programs have the potential to increase reach and early studies reveal modest impact.³ Less impressive outcomes have been produced by commercial weight loss mobile apps perhaps because they focus mostly on self-monitoring which in spite of being an essential component of behavioral weight loss interventions, has poor efficacy as a standalone intervention.^{4,5} Comprehensive technology-based weight loss programs typically use online platforms to provide 1) technology supported dietary self-monitoring, 2) counseling in behavioral strategies, and 3) access to a peer group. In these models, the only technology-supported behavioral strategy is usually self-monitoring. The remaining behavioral strategies are the responsibility of counselors who provide personalized feedback. Technology that can assist people in the implementation of a wider range of behavioral strategies could increase the efficacy of technology-supported interventions. In separate studies, we developed and tested the feasibility of an online weight loss intervention and two mobile apps that help participants implement two behavior change strategies (problem solving and stimulus control).

Aims

The goal of this study is to merge these technologies into a comprehensive technology-delivered weight loss intervention and add new features that were suggested during our user-centered design process. Aim 2 of this grant is the pilot feasibility randomized trial. The goal is to evaluate feasibility of a program where participants will all receive an online weight loss program delivered via a private Facebook group led by a professional counselor but be randomized to the Habit app which we developed or commercial calorie tracking app. These apps would serve as a tool to participants during the intervention (we are not assessing the efficacy of the app on participants weight loss). Feasibility outcomes are recruitment, retention, app use, engagement, acceptability, burden, group cohesion, and contamination at 6 months. Our goal is to evaluate whether we meet our targets for these outcomes.

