The total number of participants that will be enrolled into the 6-month feasibility trial is 70. It is estimated that we will screen ~1,700 participants to achieve this recruitment goal. Since the initial contact is via an online link, there will be many incomplete responses driving up the number of screened-out participants.

How was sample size determined?

We based the sample size of 70 for this pilot feasibility trial on necessities for examining feasibility. This sample size allows us to recruit online groups of 35 which we have demonstrated in an ongoing study is feasible and breeds regular engagement. Our previous work with smaller online groups (i.e., n=12)^{33,34} showed that presence of a few quiet participants can result in a fairly rapid decline engagement among entire group.^{33,34} We plan on enrolling waves of 70 participants (35 participants in each treatment condition), thus the feasibility trial allows to pilot recruitment procedures and assess feasibility of recruitment and engagement in the Facebook groups.

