Problem Solving Feature. Participants will be asked to do problem solving. The participants will click on the ‘problem solving’ tab on the main screen and then selects ‘solve a diet problem or ‘solve an exercise problem’, the next screen will ask them to identify their biggest problem with diet/exercise and then they will answer a series of questions to help the app provide tailored solutions to the participants. Participants will then pick a solution to work on for that week. They can access their current solution they are working on as well and set a reminder and access previous solutions worked on under the ‘problem solving’ tab in the app.

Weekly Check-ins. Participants will report their weight and if they accomplished scheduled solutions in the weekly check in. They can continue working on the same problems and solutions and/or select new ones. Participants who lost no weight will be prompted to try a new solution. Participants who have lost no weight but have accomplished their solutions will be prompted to select a new problem to work through. This will prevent participants from putting more energy into solving problems that when solved do not result in weight loss and to nudge them toward problems that when solved will result in weight loss. If a participant hasn’t lost weight and has not executed their chosen solutions, they will be prompted to change the solution. This will help dislodge participants who are stuck. It might also prevent them from abandoning the app when a plan isn’t working by guiding

them on what to do when stuck. The essence of problem solving is to keep iterating on new solutions until something works, so the app keeps the participant moving through that process.

Habit App Integration with the Facebook Group

Problem Sharing in the Group. When participants select a problem from the app but do not find a desirable solution, the app will provide an option for them to share the problem with others. The prompt will provide language the user can edit as they see fit (e.g., “I am working on [nighttime snacking]! I welcome ideas! Thanks!”). This will be copied onto the clipboard on their phone and then the participant can go into the Facebook group and post it.

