Sharing Plans to Implement Solutions in the Group. Participants can also share their chosen solution with the Facebook group by clicking a button that brings up a dialogue box to edit (e.g., “I plan on [bringing my lunch to work] this week. My reminders are set for [7pm Sunday – Thursday]. Ask me how I’m doing this week!”). They can then press the “share” button which will copy the sentences from the dialogue box onto their clipboards on their phones. They can then go into the Facebook group and paste and post the language that was curated in the Habit app.

Sharing Successes in the Group. In the Habit app, when participants have successfully solved a problem and lost weight, they will have the opportunity to click a button to edit and then copy the wording in the Habit app onto their clipboard on their phone to share to the Facebook group.

Weigh-ins.

Participants will receive a Fitbit Aria scale mailed to them by the study team. This will allow them to take their weight weekly and at assessments. Weight is logged directly from the scale to the Fitbit app. Using a Wi-Fi scale will allow for a standard weight measure for each participant with a higher level of accuracy than self-reported weight. Weight is logged directly from the Fitbit scale to the participants’ Fitbit account. Participants will be asked to set up a Fitbit account for the study and share login with the study staff so that the staff can record the weight taken. Study staff help the participants set-up their Fitbit scale if they need it and check their BMI once the scale is working. If a participant has a BMI under 27, we exclude them from the study, and allow them to keep their scale as compensation. At the end of the study participants will be allowed to keep their scale and instructed to change their Fitbit password. If they already have a Fitbit account and choose not to create a 2nd one for the study, they may choose to share that login with the study staff. If they choose not to share their login for the duration of the study, they will be allowed to upload

screenshots of their weight to a secure REDCap link. Study staff will delete the screenshot from REDCap once the weight has been logged into the record.

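### Each condition is one Facebook group of 35, so condition and group coincide; the between-condition analyses and the 0.68 SD figure assume independent participants without saying so

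*Combined protocol and SAP*

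**What the plan says.** **Structure.** The enrollment statement reads: "The total number of participants that will be enrolled into the 6-month feasibility trial is 70". Under How was sample size determined?, a wave is also 70, split 35 and 35, and the online groups are to hold 35. Under Intervention, 2. Facebook Group: "The Habit and calorie tracking app conditions will each have their own Facebook group". Participants are randomized individually, but counseling, goal setting, weigh-in posts, peer exchange and the monthly sessions all run through the group.

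**Analyses.** The Analytic Plan compares conditions by ANOVA on app compliance, burden, and group cohesion and climate, and by mixed models on weight and weight loss problem solving. The only correlation it models is within-subject. Clustering by group, an ICC and a design effect are not mentioned anywhere.

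**Power.** The exploratory-outcomes text in the sample size section gives 80% power for 0.68 SD, or 4.1% weight loss if the SD is 6.0%.

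**Existing caveats.** Aims says of the apps: "we are not assessing the efficacy of the app on participants weight loss". The sample size section classes weight, problem solving, counselor time and group cohesion as exploratory and leaves efficacy to a later, fully powered trial. For app compliance the Analytic Plan says: "Exploratory analyses using ANOVAs will compare conditions on app compliance scores at 6 months". The burden ANOVA has no such label.

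**The concern.** With one group per condition, any difference between conditions is a difference between two programs plus whatever distinguishes these two sets of 35 people who interacted for six months. A participant-level standard error captures variation between people within a group. It does not capture variation between groups.

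The protocol gives its own reason to expect dependence. In its earlier groups of 12, a few silent members were enough to pull down activity across the whole group. That remark concerns engagement in smaller groups, so it supplies no ICC for weight or burden, but it does mean independence should not be assumed silently.

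The list of outcomes in Aims reads: "Feasibility outcomes are recruitment, retention, app use, engagement, acceptability, burden, group cohesion, and contamination at 6 months". Three of these eight (app use, burden, group cohesion) receive a between-condition test, two of them under an exploratory label. Group cohesion is the plainest case, since it describes the group and is compared as one group against one. The pilot is meant to inform a later efficacy trial, so a small p-value mistaken for an app effect could carry into that design.

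**Working it through.** **Inputs from the documents.** 70 participants; 35 per condition; online groups of 35; a separate group for each condition; 80% power; SD 6.0%; about 30 per condition available at 85% retention.

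**Assumed.** Two-sided alpha of 0.05: the plan gives neither alpha nor sidedness for the 0.68 SD figure, but uses 95% intervals in the same section. ICCs of 0, 0.01, 0.02 and 0.05, for illustration only.

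**1. Groups per condition.** 70 / 35 = 2 groups for 2 conditions, so 1 each. Between-group degrees of freedom = 2 − 2 = 0.

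**2. The plan's own figure.** For a two-sample t-test with independent participants, df = 68 and the noncentrality is d / √(2/35). Solving for 80% power gives d = 0.679 SD, and 0.679 × 6.0% = 4.08% (stated: 0.68 SD and 4.1%). With 30 per arm the result would be 0.736 SD. The stated figure thus matches 35 per arm, no dropout and no within-group correlation. The arithmetic is right; the independence assumption is unstated.

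**3. Effect of within-group correlation.** Set the total variance to 1, with ICC between groups and 1 − ICC within. With n per group and no app effect:

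- true variance of the difference in means: 2 × [ICC + (1 − ICC)/n]
- variance the participant-level test expects: 2 × (1 − ICC)/n
- ratio: R = 1 + n × ICC/(1 − ICC)
- type I error: 2 × P(T(2n−2) > t(0.975)/√R)

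For n = 35 and ICC 0.05: R = 1 + 35 × 0.05/0.95 = 2.84 and √R = 1.69. The critical value 1.996 is in effect reduced to 1.18, which gives 24.1%.

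| Assumed ICC | R, n = 35 | Type I error, n = 35 | Coverage of nominal 95% interval, n = 35 | Type I error, n = 30 |
|---|---|---|---|---|
| 0 | 1.00 | 5.0% | 95.0% | 5.0% |
| 0.01 | 1.35 | 9.1% | 90.9% | 8.5% |
| 0.02 | 1.71 | 13.2% | 86.8% | 12.0% |
| 0.05 | 2.84 | 24.1% | 75.9% | 21.8% |

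Simulation with 200,000 runs agrees to within 0.1 percentage point. These rates apply when the result is read as an app effect or extended to new groups. For weight and problem solving the ICC refers to the change score, and the table carries over only approximately to the mixed model on weekly weights.

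**4. Can the analysis repair it?** No. A random effect for group needs replication of groups within condition, and there is none.

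**The case against.** The strongest reply is that the plan never claims an app effect. It compares conditions, and the conditions are programs. Group activity is partly built into the Habit program: when no listed solution appeals, "the app will provide an option for them to share the problem with others", and "Participants can also share their chosen solution with the Facebook group". Because individuals were randomized, the contrast is interpretable for the two programs as delivered in these two groups. The aim is to check feasibility targets, and the plan already defers efficacy.

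Most of this stands, and it limits the size of the point. It does not remove it. The Aims disclaimer covers weight loss only. The sample size caveat defers efficacy and warns of low power, but low power warns about missed differences. It does not say that a small p-value may reflect which people shared a group.

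A reader might infer that all between-condition tests should be barred while intervals are kept. That does not follow: a p-value and an interval conditional on these two groups use the same standard error, so both are acceptable under the same caveat. Group cohesion is the exception, because the quantity belongs to the group.

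A reader might also take 24% as the trial's actual error rate. Nothing in the documents favors an ICC of 0.05 over 0, and at 0 nothing changes.

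**Conclusion.** The point holds as a minor one. Condition and Facebook group coincide, the planned comparisons and the 0.68 SD figure assume independent participants, and the documents do not say so. With positive within-group correlation, type I error for an app-level or new-group reading rises from 5% to 9%, 13% or 24% at assumed ICCs of 0.01, 0.02 or 0.05 with 35 per group. This rests on those ICCs, an assumed two-sided alpha of 0.05 and a simple two-sample comparison.

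The feasibility targets do not depend on these tests. App compliance, weight, problem solving and group cohesion are already labelled exploratory; only burden is not.

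Two further inferences are not supported. The 0.68 SD figure is not a miscalculation, since it reproduces. Nor does the overlap undermine the sample size: a larger detectable difference only reinforces the plan's own statement that it is not powered for efficacy.

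**What to change.** 1. **Analytic Plan.** Add text such as: *Each condition is delivered in one Facebook group, so condition and group coincide. Between-condition estimates, intervals and any p-values for app compliance, burden, weight and problem solving are exploratory program-plus-group contrasts, conditional on these two groups. They will not be interpreted as effects of the app alone or generalised to new groups.* Label the burden ANOVA exploratory.
2. **Group cohesion.** Replace the ANOVA, in both places where the Analytic Plan lists it, with a descriptive report of cohesion and climate total and subscale scores by group.
3. **How was sample size determined?** Add: *The 0.68 SD (4.1%) figure assumes independent participants. The detectable difference is larger if members of the same Facebook group are positively correlated, and one group per condition cannot estimate that correlation.* No adjusted figure should be printed, because the documents give no ICC.

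The cost is the cohesion p-value and a less favorable reading of the stated detectable difference. Design, sample size and data collection do not change.
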